4.2.5. Blinding/Masking

This is an unmasked study.

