4.2.7. Primary Outcome

Hypoxemic episodes (defined as SpO2 <85% for \geq 10s) will be determined by analysis of stored physiologic data.

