4.3. POTENTIAL RISKS AND BENEFITS TO SUBJECTS

Potential Risks:

This study is primarily an observational study (Aim 1), and comparative effectiveness research (Aims 2 and 3), and is hence of low risk. Infants enrolled in this study are intrinsically at high risk, as they are born extremely preterm with a risk of death exceeding 20% and death or disability exceeding 50%, but participation in this study adds only minimally to the underlying risk.

For Aim 1, we will collect physiologic data from patient monitors, and clinical data on patient characteristics, illness severity, and outcomes from the medical records of the 120 enrolled infants. The primary risks are those of loss of confidentiality and privacy. Results and their linked clinical data will then be assigned an unique identifying code and anonymized to minimize risks to confidentiality. Only the PI and research coordinator will have access to patient data before anonymization. No patient identifiers will therefore remain in the data set that will be transmitted to the Data Coordinating Center.

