5.1. STATISTICAL ANALYSIS PLAN

It should include a plan for analysis of primary and secondary outcomes, subgroup analyses if planned, and for handling of missing data and subjects who die or are lost to follow-up.

Primary Outcome:

Hypoxemic episode (SpO2 <85% for >10s) frequency

Secondary Outcome(s)

Frequency of Hypoxemia (SpO₂<85%), Bradycardia (HR<100/min), Bradycardia episode (HR<100/min for \geq 10s); Apnea (RR=0 for >20s, or RR=0 for \geq 10s + SpO2 <85% or HR<100/min); BPD defined using physiologic definition at 36w PMA

Aim 1: Statistical calculations will be performed using SPSS. Parametric tests will be used for analyses of all continuous variables except for comparisons involving the incidences of specified ranges of IBIs, which is a skew distribution. Nonparametric tests will also be used for analyses of ordinal datasets. The Kolmogorov-Smirnov (one-sample) and Friedman's and Wilcoxon signed-rank tests will be used for the nonparametric analyses. For factorial analyses of parametric data, separate repeated-measures ANOVAs will be used. For factors with more than two levels, the Greenhouse-Geisser correction will be used, and ε with unadjusted degrees of freedom will be reported. Where a main effect was observed for factors with more than two levels, post hoc tests using the Bonferroni adjustment will be done. Values will be expressed as means and SD, and *p* values (2-tailed) of <0.05 considered statistically significant. Pearson product-moment correlation coefficient analysis will be used to establish the association between pathological pauses in breathing and breathing stability.

Aims 2 and 3: As in Aim 1, we will quantify IBI and IBI variability as defined earlier (2, 4). Also as in Aim 1, other outcomes will include (i) hypoxemic time –the % time with $SpO_2 <90\%$, (ii) moderate hypoxemic time with $SpO_2 <80\%$ and severe hypoxemic time with $SpO_2 <60\%$ (iii) bradycardic time – % time with HR <100, (iv) severe bradycardic time – % time with HR <60, (iv) hypoxemic, bradycardic, or apneic episodes – the number of episodes of $SpO_2 <90\%$, $SpO_2 <80\%$, $SpO_2 <60\%$, HR<100, HR<60, or RR=0, respectively, for >10 seconds, with the episode length defined as the number of seconds of data values below the threshold, (v) cerebral hypoxemic episodes (decrease in $r_cSO_2 <50\%$ or of 20% from baseline for >1 minute) and somatic hypoxemic episodes (decrease of 20% from baseline in peri-renal area).

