5.2. SAMPLE SIZE AND POWER ESTIMATES

Aim 1: A sample size of 100 infants per group is sufficient to detect a 20% change in a parameter related to an outcome using standard parametric or nonparametric tests (e.g. Wilcoxon signed-rank) at 80% power, α =0.05, with expected standard deviation of change of 50%. We plan to enroll 120 to account for attrition due to early death. Statistical power of 80% for detecting 20% difference in parameters is maintained even if the incidence of outcome (e.g. BPD) is only 20% of enrolled (24 of 120) infants if the standard deviation is 40% or less (as is expected to be, based on preliminary studies).

Aim 2: A sample size of 16 infants is sufficient to detect a 30% change in a parameter related to an outcome using standard parametric (e.g. paired t-test) or nonparametric tests at 80% power, α =0.05, with expected standard deviation of change of 40%. Hence, enrollment of 25 patients will be sufficient, even if there is attrition of up to 5 patients due to death, and data from 4 patients has technical issues with usability.

Aim 3: As in Aim 2, 16 infants are sufficient to detect a 30% change in a parameter related to an outcome by standard parametric (e.g. paired t-test) or nonparametric tests at 80% power, α =0.05, with expected standard deviation of 40%. Hence, enrollment of 25 patients will enable detection of even minimal changes, or of changes in parameters with much variation.

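### Neither Aim 2 nor Aim 3 masks signal cleaning or usability exclusions; in Aim 2, result-related loss of the 4 recordings allowed for could raise type I error from 5% to about 6–11%, and to 38% at worst

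*Combined protocol and SAP*

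**What the plan says.** Section 4.2.5 (Blinding/Masking) is a single sentence: "This is an unmasked study". It does not separate those who deliver the interventions from those who process the recordings.

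Section 4.2.7 says that hypoxemic episodes "will be determined by analysis of stored physiologic data". The outcome is therefore derived after the event, from files.

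Section 5.2 (Aim 2) enrols 25 infants and regards this as enough even with up to 5 deaths and if "data from 4 patients has technical issues with usability". The Aim 3 paragraph also enrols 25 against 16 needed, but gives no number for deaths or unusable recordings.

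On who handles the data, Section 4.2.10 has the principal investigator, the research coordinator or a designee run or supervise the Aim 2 and 3 interventions. Section 4.3, in its Aim 1 paragraph, says: "Only the PI and research coordinator will have access to patient data before anonymization". That step removes patient identifiers; nothing is said about period labels.

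No section gives criteria for artefact or usability in Aims 2 and 3, or names who applies them. Section 4.2.4 refers filtering to cited methods, under Aim 1. Section 5.1 still carries the template instruction to describe missing-data handling, and no plan follows it.

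**The concern.** Each infant in Aims 2 and 3 serves as its own control, so the treatment comparison rests on a small set of within-infant differences. Two decisions stand between the raw signal and those differences: which segments are artefact, and which recordings are unusable. If the person deciding can see which period is which, and can see or guess the episode counts, the decisions can drift toward the expected answer without any intent to mislead.

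The exposure is largest where losses are expected. In Aim 2 the allowance is 4 of 20 surviving infants, one in five, with no written rule for identifying them. With 16 infants in the analysis, a few result-related losses can change the conclusion. Masking the file-based steps would close this route, and because the outcome comes from stored data it is feasible even though the bedside is open.

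**Working it through.** **Inputs**

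- Aim 2 effect and evaluable number (Section 5.2): "A sample size of 16 infants is sufficient to detect a 30% change in a parameter related to an outcome".
- Aim 2 variability (Section 5.2): "with expected standard deviation of change of 40" per cent.
- Aim 2 power (Section 5.2): "nonparametric tests at 80% power", α = 0.05.
- Sidedness: two-tailed, stated in Section 5.1 under Aim 1; assumed here for Aims 2 and 3.
- Aim 2 losses (Section 5.2): 25 enrolled, up to 5 deaths, 4 unusable.
- Degree of selection: not in the documents; assumed and varied below.

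**Step 1. The plan's own figure.** The standardised effect is 30/40 = 0.75. The normal approximation, n = [(z₀.₉₇₅ + z₀.₈₀) × 40/30]², gives 13.95, so 14. For the paired t-test, power is P(|T| > t₀.₉₇₅,ₙ₋₁), where T is noncentral t with n − 1 degrees of freedom and noncentrality 0.75√n:

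- n = 14: 73.7%
- n = 15: 77.1%
- n = 16 (noncentrality 0.75 × 4 = 3): 80.06%

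The smallest n reaching 80% is 16, as the plan states. The attrition chain also closes: 25 − 5 − 4 = 16. A one-sided test would already give 84.4% at n = 14, so 16 fits a two-sided test.

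**Step 2. Model for the exclusions.** Take 20 infants (25 − 5), one normal paired difference each, true mean 0, SD 40. Remove 4 and apply a two-sided paired t-test at 0.05 to the remaining 16. Each scenario uses 200,000 simulated trials; the Monte Carlo standard error at 38% is √(0.38 × 0.62/200,000), about 0.1 percentage point.

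For partial selection, each infant gets a score s = r·d + √(1 − r²)·e, where d is the standardised difference (higher is more favourable) and e is independent noise. The 4 lowest scores are dropped. So r = 0 is result-independent loss and r = 1 is removal of the 4 least favourable infants.

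**Step 3. Results with no true effect, 4 of 20 dropped**

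| How the 4 are lost | Two-sided error | In favourable direction | Spurious mean change (points, SD 40) |
|---|---|---|---|
| Independently of result | 5.0% | 2.4% | 0.0 |
| Correlation 0.2 | 5.8% | 4.5% | 2.7 |
| Correlation 0.3 | 6.9% | 5.9% | 4.0 |
| Correlation 0.5 | 10.7% | 10.2% | 6.6 |
| Correlation 0.7 | 17.7% | 17.4% | 9.3 |
| 1 least favourable, 3 random | 8.0% | 6.6% | 3.9 |
| 2 least favourable, 2 random | 14.4% | 13.7% | 7.2 |
| 4 least favourable (worst case) | 38.0% | 37.8% | 13.3 |

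As a check, the shift should scale with r: 0.2 × 13.3 = 2.7 and 0.5 × 13.3 = 6.7, against simulated 2.7 and 6.6.

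**Step 4. Sensitivity of the worst case.** If only the least favourable 1, 2 or 3 of 20 are dropped and no others, two-sided error is 8.8%, 16.1% and 26.3%. With no deaths and the worst 4 of 25 dropped, it is 34.4%.

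**Step 5. After the fix.** If masking makes the 4 losses independent of the result, error returns to 5.0% and power at n = 16 is the planned 80.1%. If no recording is dropped, power at n = 20 is 88.9%.

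The simulation covers loss of whole infants only. Bias from artefact rejection within a recording is not quantified.

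**The case against.** The strongest reply has four parts.

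*Much of the processing is already fixed.* Sections 4.2.7 and 4.2.8 set numeric event thresholds, Section 4.2.4 restricts the Aim 3 analysis to the second 12 h of each period, and filtering is referred to cited methods. This stands as far as it goes: how much discretion the cited methods leave cannot be judged from the documents. But a threshold does not decide which segments or infants reach the count. Section 4.3 calls Aim 2 intent-to-treat, but there it is discussing whether the intended change in carbon dioxide is achieved, not which recordings are kept.

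*The 4 recordings are a contingency, not a licence.* This is right. A reader might infer that the plan permits someone to choose 4 recordings to drop, in both aims. The text supports neither half: the number is an attrition assumption in a sample-size argument, and it appears for Aim 2 only.

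*The plan does not say that unmasked people make the exclusions.* Also right. A reader might combine Sections 4.2.10 and 4.3 and conclude that the staff who run the interventions will also judge usability. The plan is silent on who decides, and the access statement sits under Aim 1. The defect is that nothing prevents it.

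*The large error figure needs deliberate selection.* It does. 38% requires that exactly the 4 least favourable infants are removed. Weaker dependence gives far less, and unmasked but result-independent exclusion does no harm to type I error.

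**Conclusion.** The point holds. The whole study is declared unmasked although the file-based steps could be masked, and neither Aim 2 nor Aim 3 protects artefact rejection or usability decisions by masking or by written criteria.

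For Aim 2, if the 4 recordings allowed for are lost in a way related to the result, two-sided type I error rises from 5% to about 6% to 11% for an assumed correlation of 0.2 to 0.5, with 38% as the ceiling. This rests on normal paired differences, one per infant, 20 infants before exclusion and a two-sided 0.05 test. The degree of selection is assumed throughout.

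Two stronger conclusions are not supported. One is that the trial's false-positive rate is 38%: that is a bound, not an estimate. The other is that the same figures describe Aim 3: it has the same masking gap, but no stated number of unusable recordings from which to calculate.

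**What to change.** In Section 4.2.5, state that caregivers are unmasked, and that artefact rejection, usability decisions and episode counts for Aims 2 and 3 are made on files with coded period labels and without the TcCO2, ventilator and oxygen-setting channels.

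In Section 5.1, write the usability and artefact criteria in advance, say who applies them, and require that exclusions and counts are locked before labels are released. Add a sensitivity analysis that includes all recordings. The written criteria and the sensitivity analysis limit the bias even where masking is incomplete.

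**Cost.** No extra infants are needed and bedside care is unaffected, but the change is not free. The anonymisation in Section 4.3 removes identifiers rather than period labels, and Aim 1 uses the same recordings with their TcCO2, ventilator and oxygen data (Section 4.2.4). Aims 2 and 3 therefore need a separate coded extract and some added analysis work. Masking may be imperfect in Aim 2: the intervention works through ventilator rate or pressure, so the respiratory-rate channel may partly reveal the period.

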4.2.6. Control or Monitoring of Co-interventions

Medical interventions and ventilator management will be based upon clinician discretion. Evidence and consensus based guidelines are followed for uniformity in practice. No changes in management are required for this observational cohort study, except for the duration of the intensive multiparametric monitoring for 96 hours at 2 weeks postnatal age, 32 weeks PMA, and 36 weeks PMA, when interventions will be performed as described in Aims 2 (minor changes in TcCO2) or Aim 3 (Nasal cannula or Servo-controlled O2 environment).

4.2.7. Primary Outcome

Hypoxemic episodes (defined as SpO2 <85% for \geq 10s) will be determined by analysis of stored physiologic data.

4.2.8. Secondary Outcomes (*if applicable*)

- 1. Hypoxemia defined as SpO2 <85%
- 2. Bradycardia defined as HR <100/min
- 3. Bradycardic episode as HR <100/min for >10s
- 4. Apnea defined as RR=0 for >20s, or RR=0 for >10s + SpO2 <85% or HR <100/min
- 5. BPD defined using physiologic definition at 36w PMA

4.2.9. Additional Safety Outcomes (if applicable)

Infants will be monitored for severe apnea/bradycardia episodes (defined as requiring bag and mask ventilation for >30 s or chest compression) associated with interventions in Aims 2 and 3. No such episodes were found to be associated with the interventions in pilot studies.

4.2.10. Compliance Monitoring

No specific protocol exists for Aim 1 (observational study). The PI or Research Coordinator or designee will initiate/stop or personally supervise the interventions in Aims 2 and 3. In pilot studies of interventions used in Aims 2 and 3, no issues with maintenance of compliance were noted.

4.2.11. Study Specimens

No biofluid specimens are required for the single-center study, but will be considered in the multicenter protocol.

4.2.12. Post-hospital Procedures

Reminder for follow-up and instructions for follow-up at 3 months will be sent to parents/caregivers.

4.2.13. Follow-up at 3 Months

Survivors to discharge will be followed-up at the 3 month follow-up visit for a sleep study (polysomnographic study) at the Children's of Alabama sleep center by the Pediatric pulmonologist. Respiratory outcomes as in SUPPORT Breathing Outcomes study (30) will be evaluated at the 3 month follow-up visit in addition to the Sleep study.

4.2.14. Additional Follow-up Assessments

This will be decided upon by regular clinical team. Most infants enrolled in this study are eligible for follow-up by the Newborn Follow-Up clinic, and some are also eligible for follow-up by the BPD follow-up clinic.

4.3. POTENTIAL RISKS AND BENEFITS TO SUBJECTS

Potential Risks:

This study is primarily an observational study (Aim 1), and comparative effectiveness research (Aims 2 and 3), and is hence of low risk. Infants enrolled in this study are intrinsically at high risk, as they are born extremely preterm with a risk of death exceeding 20% and death or disability exceeding 50%, but participation in this study adds only minimally to the underlying risk.

For Aim 1, we will collect physiologic data from patient monitors, and clinical data on patient characteristics, illness severity, and outcomes from the medical records of the 120 enrolled infants. The primary risks are those of loss of confidentiality and privacy. Results and their linked clinical data will then be assigned an unique identifying code and anonymized to minimize risks to confidentiality. Only the PI and research coordinator will have access to patient data before anonymization. No patient identifiers will therefore remain in the data set that will be transmitted to the Data Coordinating Center.

For Aim 2, we will enroll a subset of infants from Aim 1 to determine if mild permissive hypercapnia (trying to increase blood carbon dioxide concentrations 5 mm Hg from baseline) leads to improved control of breathing in preterm infants. While extreme hypercapnia associated with pH <7.15 is generally avoided, mild hypercapnia with pH maintained >7.2 is usual practice in most centers, including UAB, and is considered safe. These infants will be monitored using continuous pulse oximetry and transcutaneous CO₂ monitoring, and the fluctuations in blood carbon dioxide concentrations of 5 mm Hg from baseline are expected to alter blood pH by less than 0.05, and these fluctuations are much less than normally noted in routine care (fluctuations of up to 30 mm Hg or more over a day are often seen). We will not include infants with extreme blood carbon dioxide concentrations (blood PCO₂ of less than 40 mm Hg or more than 70 mm Hg as indicated by transcutaneous monitoring, after adjustment for skin-blood PCO₂ difference on most recent blood gas analysis). This Aim is intent-to-treat, and it is possible that we will not see any statistical differences over time with regards to blood carbon dioxide concentrations despite our intent to increase or decrease the level by 5 mm Hg, as there are large fluctuations in routine care, due to inherent variation in respiratory drive and other clinical variables. Even more extreme transient elevations of blood carbon dioxide at 2 weeks of age are unlikely to cause clinical problems as the risk period of IVH (the main concern with elevated blood carbon dioxide in preterm infants) is mainly in the first few days after birth. Hypocapnia or very low blood carbon dioxide concentrations may reduce brain blood flow, but we are evaluating infants with levels in the upper end of the normocapnia range or mild permissive hypercapnia, and excluding infants with more extreme values. Infants with hypocapnia generally have spontaneous hyperventilation rather than due to clinician intervention, as the goal is minimal ventilation and not overventilation.

For Aim 3, we will evaluate the effects of oxygen administration using a servo-controlled oxygen environment as compared to nasal cannula on control of breathing and stability of blood oxygen levels. Both methods are in common use in our NICU, and are not known to have any major risks. Minor risks of using a nasal cannula include accidental dislodgement with movement of the infant. Minor risks of oxygen environment include a drop in oxygen concentration if caregivers leave port-holes open for too long by accident, allowing the oxygen to exit the incubator. However, as infants are being carefully monitored using continuous pulse oximetry and ECG monitoring, any desaturation or bradycardia episode will immediately lead to an audible and visible alarm.

We also plan to develop a biorepository using remnant samples, as required by the multicenter collaborative (no invasive sampling will be done specifically for this study).

There is no financial risk from participation in this study.

A potential risk is of psychological harm to parents during the informed consent process, as they become aware of the high risk of death or handicap to their very preterm infant. However, this risk is the same, whether or not the parents are in the study, as they all receive counseling regardless of being in this or other studies.

	Risk:	Frequency	Severity	r Reversibility
1.	Loss of confidentiality and privacy	Very low (anonymized data)	Low	Not applicable

- 2. Mild increases or decreases in PCO2 Common (happens often routinely) Low Reversible
- 3. Nasal cannula dislodgement

Common (happens often routinely) Low Reversible

- 4. Oxygen environment open to air Common (happens often routinely) Low Reversible
- 5. Psychological harm to parents Common (all parents at risk) Low Not applicable

This study is an observational study (Aim 1) and comparative effectiveness study (Aims 2 and 3), and the risks that the infants are exposed to are those that are normally present and happen often in usual neonatal intensive care. As this study involves more intensive monitoring than usual, the expectation is that these infants will be at even lower risk as compared to infants who are monitored only using standard equipment. The minor risks in Aims 2 and 3 occur frequently in infants during usual intensive care, and are likely to be unchanged in this study compared to usual care, but harm may occur if nursing staff do not respond to monitoring alarms (as in usual care). The more intensive monitoring may help reduce these risks.

Potential benefits:

There is a potential of direct benefit to study participants from participating as Aim 1 is based on intensive multi-parametric monitoring of multiple variables only some of which are routinely monitored. As the monitoring is not masked to caregivers, nurses and clinicians may become aware of changes in the monitored variables and intervene more quickly for abnormal cardiorespiratory events and prevent apnea or bradycardia duration in the infants who are enrolled and being monitored, as compared to infants who are not enrolled.

Aims 2 and 3 are comparative effectiveness research studies done in a cross-over fashion, so infants are not likely to have a persistent benefit from one intervention. If caregivers note that one intervention seems to be associated with better oxygen saturation stability, fewer apneic episodes etc, it is possible that these infants may benefit by the better intervention being used after the period of evaluation for Aim 2 or 3.

The results of this study will be published in the peer-reviewed literature and then deposited in PubMed Central to make the manuscript freely available, which may benefit other investigators in the field as well as interested parents and family.

Development and validation of mathematical models of personalized ventilatory patterns based on multiparametric vital signs monitoring and signal analysis methods will enable the scientific community to gain greater insight into the pathogenesis of respiratory disorders in extremely preterm infants and discover targets for new prevention and treatment strategies to improve outcomes for very vulnerable children at the beginning of life

SECTION 5. ANALYTICAL PLAN

